13.1. Informed Consent

The investigator is responsible for ensuring that the patient understands the potential risks and benefits of participating in the study, including answering any questions the patient may have throughout the study and sharing in a timely manner any new information that may be relevant to the patient's willingness to continue his or her participation in the trial.

The ICF will be used to explain the potential risks and benefits of study participation to the patient in simple terms before the patient is entered into the study and to document that the patient is satisfied with his or her understanding of the potential risks and benefits of participating in the study and desires to participate in the study.

The investigator is ultimately responsible for ensuring that informed consent is given by each patient before the study is started. This includes obtaining the appropriate signatures and dates on the ICF prior to the performance of any protocol procedures and prior to the administration of the investigational product.

13.2. Ethical Review

Lilly or its representatives must approve all ICFs before they are used at investigative sites. All ICFs must be compliant with the ICH guideline on GCP.

Documentation of ERB approval of the protocol and the ICF must be provided to Lilly before the study may begin at the investigative site(s). The ERB(s) will review the protocol as required.

The study site's ERB(s) should be provided with the following:

- the current IB and updates during the course of the study
- ICF
- relevant curricula vitae.

13.3. Regulatory Considerations

This study will be conducted in accordance with:

- 1) consensus ethics principles derived from international ethics guidelines, including the Declaration of Helsinki and Council for International Organizations of Medical Sciences (CIOMS) International Ethical Guidelines
- 2) the ICH GCP Guideline [E6]
- 3) applicable laws and regulations.

The investigator or designee will promptly submit the protocol to applicable ERB(s).

Some of the obligations of the sponsor will be assigned to a TPO.

An identification code assigned to each patient will be used in lieu of the patient's name to protect the patient's identity when reporting AEs and/or other trial-related data.

13.3.1. Investigator Information

Site-specific contact information may be provided in a separate document.

13.3.2. Protocol Signatures

The sponsor's responsible medical officer will approve the protocol, confirming that, to the best of his or her knowledge, the protocol accurately describes the planned design and conduct of the study.

After reading the protocol, each principal investigator will sign the protocol signature page and send a copy of the signed page to a Lilly representative.

Serum ixekizumab PK sample ^h		PreD	X	X	X	X	X	X	X	X	X	X	X	X
QIDS-SR ₁₆	X													
C-SSRS		PreD	X	X	X	X	X	X	X	X	X	X	X	X
PASI	X	PreD					X			X		X	X	X
sPGA	X	PreD					X			X		X	X	X
Clinical chemistry, electrolytes, hematology ⁱ	X	PreD			X		X		X	X				X
High-sensitivity C-reactive protein		PreD					X			X				X
Urinalysis	X	PreD			X					X				X
Serum for anti-ixekizumab antibody		PreD			X		X		X			X		X
Urine pregnancy test ⁱ	X	PreD								X				X

Study Schedule Protocol I1F-MC-RHBN—Single-Dose Phase

Abbreviations: C-SSRS = Columbia-Suicide Severity Rating Scale; ECG = electrocardiogram; h = hour(s); PASI = Psoriasis Area and Severity Index; PK = pharmacokinetics; PPD = purified protein derivative; PreD = prior to dose; QIDS-SR₁₆ = Quick Inventory of Depressive Symptomatology–Self Report, 16 item; QTF = QuantiFERON[®]-TB Gold test; sPGA = static Physician’s Global Assessment; TB = tuberculosis; T-SPOT = T-SPOT[®].TB test; V = visit.

Notes: Patients who withdraw from the treatment phase will have an early treatment discontinuation visit with procedures performed as shown for Visit 14. Each blood draw should be collected at approximately the same time of day as the dose administration at Week 0 (Visit 2).

- a Visit 1 procedures may be conducted over more than 1 day as long as all tasks are completed within the allowable visit tolerance (at least 3 days should be allowed for receipt of laboratory test results).
- b Weight may be recorded at other visits as clinically indicated.
- c Sitting blood pressure, respiratory rate, and pulse rate are to be obtained at approximately the same time as ECG measurements or plasma ixekizumab blood sampling. When multiple assessments are scheduled for the same time point, the order of completion should be ECG, vital signs, and then blood sampling.
- d Patients with documentation of a negative test result within 3 months prior to baseline (Week 0; Visit 2) do not need a TB screen at Visit 1.
- e See Section 10.4.3.5 for detailed description of PPD/QTF or T-SPOT testing.
- f To account for diurnal variations, ECGs should be performed at approximately the same time of day as the Visit 2 predose ECG (± 2 hours).
- g Additional ECGs may be performed as clinically indicated.
- h Each blood draw should be collected at approximately the same time of day as the initial sample taken prior to dose administration at Week 0 (Visit 2).
- i Unscheduled blood chemistry and hematology panels may be performed at the discretion of the investigator.
- j Required for all women.

**Attachment 2. Protocol RHBN Study Schedule—
Multiple-Dose Phase**

Study Schedule Protocol I1F-MC-RHBN—Multiple-Dose Phase

Period Procedure	Screening	Treatment Period															Observation Period						
		V1 ^a	V2	V3	V4	V5	V6	V7	V8	V9	V10	V11	V11A	V11B	V11C	V11D	V11E	V11F	V12	V12A	V13	V14	V15
Visit Number	V1 ^a	Randomize																					
Day Relative to Start of Study Drug	-28 to -3	1	3	5	8	11	15	22	29	43	57	59	61	64	67	71	78	85	99	113	141	169	197
Week Relative to Start of Study Drug		0		1		2	3	4	6	8	8	8	9	9	10	11	12	14	16	20	24	28	
Visit Tolerance Interval (Days)		0	0	0	0	±1	±2	±2	±2	±2	±1	±1	±1	±1	±1	±2	±2	±7	±7	±7	±7	±7	
Informed consent (before procedures/tests)	X																						
Demographics, height, weight ^b	X																						
Inclusion/exclusion review	X	PreD																					
History and/or physical examination	X	PreD								X											X		X
Concomitant medications	X	X	X	X	X	X	X	X	X	X	X							X	X	X	X	X	X
Preexisting conditions/adverse events	X	X	X	X	X	X	X	X	X	X	X							X	X	X	X	X	X
Vital signs ^c	X	PreD, 1h, 3h							X		X							X		X	X	X	X
Body temperature	X	PreD					X		X	X ^d	X												X
Chest x-ray and PPD/QTF or T-SPOT testing for TB ^{e,f}	X																						
EKG ^{g,h}	X	PreD	X	X			X		X		X												X
Study drug dosed																							
Q2W group		X					X		X	X	X												
Q4W group		X							X		X												
Serum ixekizumab PK sample ^{i,j}		PreD	X	X	X	X	X	X	X	X ^k	X	X	X	X	X	X	X	X	X	X	X	X	X
QIDS-SR ₁₆	X																						
C-SSRS		PreD	X	X	X	X	X	X	X	X	X							X		X	X	X	X
PASI	X	PreD					X		X	X								X		X	X	X	X

Study Schedule Protocol I1F-MC-RHBN—Multiple-Dose Phase

Period Procedure	Entry	Treatment Period															Observation Period						
Visit Number	V1 ^a	V2 Randomize	V3	V4	V5	V6	V7	V8	V9	V10	V11	V11A	V11B	V11C	V11D	V11E	V11F	V12	V12A	V13	V14	V15	V16
Day Relative to Start of Study Drug	-28 to -3	1	3	5	8	11	15	22	29	43	57	59	61	64	67	71	78	85	99	113	141	169	197
Week Relative to Start of Study Drug		1			2		3	4	5	7	9	9	9	10	10	11	12	13	15	17	21	25	29
Visit Tolerance Interval (Days)		0	0	0	0	0	±1	±2	±2	±2	±2	±1	±1	±1	±1	±1	±2	±2	±7	±7	±7	±7	±7
sPGA	X	PreD					X			X	X							X		X	X	X	X
Clinical chemistry, electrolytes, hematology ^l	X	PreD			X		X		X	X										X			X
High-sensitivity C-reactive protein		PreD					X			X										X			X
Urinalysis	X	PreD			X					X										X			X
Serum for anti-ixekizumab antibody		PreD			X		X		X									X			X		X
Urine pregnancy test ^m	X	PreD								X										X			X

Abbreviations: C-SSRS = Columbia-Suicide Severity Rating Scale; ECG = electrocardiogram; h = hour(s); PASI = Psoriasis Area and Severity Index; PK = pharmacokinetics; PPD = purified protein derivative; PreD = prior to dose; Q2W = every 2 weeks; Q4W = every 4 weeks; QIDS-SR₁₆ = Quick Inventory of Depressive Symptomatology–Self Report, 16 item; QTF = QuantiFERON[®]-TB Gold test; sPGA = static Physician’s Global Assessment; TB = tuberculosis; T-SPOT = T-SPOT[®].TB test; V = visit.

Notes: Patients who withdraw from the treatment phase will have an early treatment discontinuation visit with procedures performed as shown for Visit 16. Visits denoted by a letter after the visit number are visits at which the patient will visit the study site for serum ixekizumab sampling only. No other tests will be performed at these visits.

- a Visit 1 procedures may be conducted over more than 1 day as long as all tasks are completed within the allowable visit tolerance (at least 3 days should be allowed for receipt of laboratory test results).
- b Weight may be recorded at other visits as clinically indicated.
- c Sitting blood pressure, respiratory rate, and pulse rate are to be obtained at approximately the same time as ECG measurements or plasma ixekizumab blood sampling. When multiple assessments are scheduled for the same time point, the order of completion should be ECG, vital signs, and then blood sampling.
- d Body temperature should be taken only for patients in the Q2W group at this visit because patients in the Q4W group do not receive study drug at this visit.
- e Patients with documentation of a negative test result within 3 months prior to baseline (Week 0; Visit 2) do not need a TB screen at Visit 1.
- f See Section 10.4.3.5 for detailed description of PPD/QTF or T-SPOT testing.
- g To account for diurnal variations, ECGs should be performed at approximately the same time of day as the Visit 2 predose ECG (±2 hours).
- h Additional ECGs may be performed as clinically indicated.
- i Each blood draw should be collected at approximately the same time of day as the initial sample taken prior to dose administration at Week 0 (Visit 2).

- j When PK samples are scheduled at the same visits as dose administrations, then the PK sample should be taken pre-dose.
- k Only for the Q2W dosing regimen.
- l Unscheduled blood chemistry and hematology panels may be performed at the discretion of the investigator.
- m Required for all women.

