9.6. Concomitant Therapy

Patients will maintain their usual medication regimen for other concomitant diseases throughout the study unless that regimen is specifically excluded in the protocol. Patients taking concomitant medications should be on stable doses at the time of baseline and should remain at stable doses throughout the study unless changes need to be made for an AE. Additional systemic drugs are to be avoided during the study unless they are required to treat an AE. Other medications may be allowed if approved by the sponsor or its designee.

If the need for concomitant medication arises, inclusion or continuation of the patient may be at the discretion of the investigator after consultation with a Lilly clinical pharmacologist or CRP. Any additional medication used during the course of the study must be documented.

All concomitant medication taken during the study must be recorded on the concomitant medication page of the CRF. Treatment with concomitant psoriasis therapies during the study is permitted only as outlined in the Exclusion Criteria (Section 8.1.2) and as described in the following paragraphs. Patients taking permitted medications should be on chronic stable doses at the baseline visit (Week 0; Visit 2) as specified in Section 8.1.2.

The following therapies will not be permitted during the course of the study:

- psoriasis therapy as described in the Inclusion and Exclusion Criteria (Sections 8.1.1 and 8.1.2), except as described in the following paragraphs for topical agents.
- concomitant medications as described in the Inclusion and Exclusion Criteria (Sections 8.1.1 and 8.1.2)
- live vaccines
- phototherapy.

Topical Psoriasis Treatment: Topical psoriasis treatment as indicated below will be permitted after completion of Week 4 (Visit 9) and prior to Week 18 (Day 127) during the single-dose phase and after completion of the Week 12 visit during the multiple-dose phase.

- Topical treatments including, but not limited to corticosteroids, vitamin D analogues, tarzartene, and tacrolimus are permitted. Only steroids of mild potency (for example, desonide, fluocinolone acetonide, and alclometasone) or low potency (that is, hydrocortisone) are recommended for the face, axilla, and/or genitalia. These topical medications should not be used within approximately 24 hours prior to study visits requiring sPGA and PASI measures.

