5. STUDY DESIGN

Study RHBN is a Phase 1, multicenter, open-label, single- and multiple-dose outpatient study in up to 45 patients with psoriasis. A 160 mg SC starting dose (Week 0) followed by an 80 mg SC dose Q2W or Q4W was evaluated as an induction dosing regimen over 12 weeks of treatment in global pivotal Phase 3 studies in patients with psoriasis (Studies RHAZ, RHBA, and RHBC). In this study, the PK profile and safety/tolerability of ixekizumab 80 mg will be assessed initially in the single-dose phase. Thereafter, the induction dosing regimens evaluated in the pivotal Phase 3 studies will be evaluated in the multiple-dose phase for this Phase 1 study in China.

For the single-dose phase, patients will receive a single dose of ixekizumab 80 mg SC on Day 1 and will be assessed at regular visits for 20 weeks. Patients completing the single-dose phase have the option of enrolling in the multiple-dose phase after completing the final visit in the single-dose phase. Patients will remain at the site for a minimum of 4 hours postdose.

The multiple-dose phase can be initiated once 6 patients have completed the Week 6 (Day 43) visit in the single-dose phase and safety data collected through 6 weeks postdosing from these patients have been reviewed. After review of these safety data, an agreement on initiation of the multiple-dose phase will be made by the investigator and sponsor.

In the multiple-dose phase, patients will be administered a starting dose of ixekizumab 160 mg SC on Day 1 and will then be randomized into 1 of 2 dosing regimens for the 8-week treatment period: (1) 80 mg SC Q2W (at Weeks 2, 4, 6 and 8) or (2) 80 mg SC Q4W (at Weeks 4 and 8). After Week 8, patients will be assessed at regular visits for an additional 20 weeks. Patients will remain at the site for a minimum of 4 hours after the first dose and for 2 hours after subsequent doses.

Figure 1 and Figure 2 illustrate the study design for the single-dose phase and multiple-dose phase, respectively.

Single-Dose Phase

Abbreviations: D = day; SC = subcutaneous; V = visit; W = week. Note: Patients who complete Visit 14 of the single-dose phase are eligible for participation in the multiple-dose phase.

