9.6 Safety and Tolerability Assessments

9.6.1 Adverse events

Where changes in severity are recorded in the Case Report Form (CRF), each separate severity of the adverse event (AE) will be reported in the listings, only the most severe will be used in the summary tables. A pre-existing condition is defined as an AE that starts before the patient has provided the first written informed consent and is ongoing at consent. A non-treatment emergent AE is defined as an AE which starts after informed consent but prior to dosing. A treatment-emergent AE is defined as an AE which occurs postdose within the defined phase, or which is present prior to the first dosing and becomes more severe postdose within the defined phase. Treatment-emergent AEs will be assigned to the phase to which it's considered treatment-emergent. Note that for patients who participate in both phases, (i) if AEs start and end during the gap (after the end of SDP and before the start of MDP), or if AEs start during the gap and continue to the multiple-dose phase without worsening in severity, such AEs will not be considered as treatment-emergent or be analyzed, but may be noted in CSR; (ii) if AEs start in SDP and continue to MDP without worsening in severity, it will be considered as treatment-emergent in SDP, but not treatment-emergent in MDP. AEs by week of onset will be presented.

All AEs will be listed. Treatment-emergent AEs will be summarized by phase, dose regimen, severity and relationship to the study drug. The frequency (the number of AEs, the number of patients experiencing an AE and the percentage of patients experiencing an AE) of

treatment-emergent AEs will be summarized by dose regimen, Medical Dictionary for Regulatory Activities (MedDRA) version 19.1 (use the latest version of MedDRA when an updated version becomes available) system organ class and preferred term. The summary and frequency AE tables will be presented for all causalities and those considered related to the study drug. Any serious AEs will be tabulated.

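### The two pages of the multiple-dose schedule (Protocol Attachment 2) label the same study days one week apart, and Section 9.6 opens topical treatment by a bare week label

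*Protocol*

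**What the plan says.** Attachment 2 of the protocol spreads the multiple-dose schedule over two pages and repeats the column headings. Visits and study days agree on both pages; the last eight days read "71 78 85 99 113 141 169 197" (V11E to V16). The week row beneath them, headed "Week Relative to Start of Study Drug", does not agree. For those eight columns the first page has "10 11 12 14 16 20 24 28" and the second has "11 12 13 15 17 21 25 29".

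Protocol Section 9.6 uses a week label as a conduct rule. In the multiple-dose phase, topical psoriasis treatment is allowed "after completion of the Week 12 visit during the multiple-dose phase". The single-dose half of the same sentence is tied to a visit and a day: "after completion of Week 4 (Visit 9) and prior to Week 18 (Day 127) during the single-dose phase".

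Both PASI and sPGA are scheduled at Day 85. The PASI row is on the first page and the sPGA row on the second. The notes to Attachment 2 say that visits with a letter suffix, such as V11F, are for drug-concentration sampling and nothing else.

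**The concern.** Each page has exactly one Week 12 column, so each gives a definite answer to the question Section 9.6 poses, and nothing on either page tells the reader that the other differs.

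The last dose is on Day 57, so Day 85 is the first PASI and sPGA assessment scheduled after it. Section 9.6 allows corticosteroids, vitamin D analogues and tacrolimus, among others, with only a short abstention before assessment visits. SAP Section 9.4.2 summarises PASI and sPGA responses over time with no rule for topical use, and SAP Section 9.6.2 only lists concomitant medication. If sites opened topical treatment on different days, the difference would pass unadjusted into the Day 85 summaries.

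**Working it through.** **Inputs.** Visits, days, week labels and visit tolerances come from both pages of Protocol Attachment 2. The topical rule and abstention periods come from Protocol Section 9.6. Cross-checks come from the Protocol Synopsis, Sections 7.1, 8.1.1 and 9.6, Attachment 1, the footnotes to Attachment 2, and SAP Section 5.

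**Step 1: reproduce the printed labels.** The first page follows week = floor((day − 1)/7). The second follows the same formula plus 1. Selected columns:

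| Visit | Day | floor((day − 1)/7) | First page | Second page |
|---|---|---|---|---|
| V2 | 1 | 0 | 0 | 1 |
| V10 | 43 | 6 | 6 | 7 |
| V11 | 57 | 8 | 8 | 9 |
| V11F | 78 | 11 | 11 | 12 |
| V12 | 85 | 12 | 12 | 13 |
| V16 | 197 | 28 | 28 | 29 |

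All 19 visits with a week label differ by exactly one week. In the text as read from the PDF, the first-page row has lost one blank cell near its start (21 cells against 22 days). A lost or shifted cell cannot turn a series ending in 28 into one ending in 29, and the eight closing columns do not depend on it.

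**Step 2: compare with the rest of the documents.**

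- Sections 8.1.1 and 9.6, and the footnotes to Attachment 2, equate Visit 2 with Week 0. The second page calls it Week 1.
- Section 7.1 equates Week 6 with Day 43: (43 − 1)/7 = 6. The second page gives 7.
- Section 9.6 equates Week 18 with Day 127: (127 − 1)/7 = 18. The second-page formula would give 19.
- Attachment 1 labels Day 85 as Week 12. The second page of Attachment 2 gives 13.
- The Synopsis gives the multiple-dose phase 28 weeks: (197 − 1)/7 = 28. The second page ends at 29.
- SAP Section 5 has "80 mg SC Q2W (at Weeks 2, 4, 6 and 8". The second page would number those doses 3, 5, 7 and 9.

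The second-page row is the only place found that starts at Week 1.

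**Step 3: size of the gap.**

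- Nominal: 85 − 78 = 7 days.
- V11F and V12 each carry ±2 days. Shortest: (85 − 2) − (78 + 2) = 3 days. Longest: (85 + 2) − (78 − 2) = 11 days.
- The abstention of about 24 hours covers the whole first group of topical agents, not steroids alone: 7 − 1 = 6 days of possible use, range 2 to 10.
- Medicated shampoos, emollients and other nonsteroidal products have about 12 hours: 7 − 0.5 = 6.5 days, range 2.5 to 10.5.

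**The case against.** The strongest reply is that the documents largely settle the reading. The topical sentence itself counts Day 1 as Week 0, through its Week 18 and Day 127 pairing, and nearly everything else follows suit. V11F is a sampling-only visit with no entry in the concomitant-medication row, so it is an odd place to open a treatment permission. The dosing, concomitant-medication and PASI rows are all on the first page. For the rule to misfire, a site would have to take its week number from the second page alone and then act on it at a sampling visit. This stands, and it rules out treating Day 78 and Day 85 as equally supported readings.

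The reply is also right about the stakes. PASI and sPGA are exploratory and summarised descriptively. The protocol already accepts topical use alongside scheduled assessments: the single-dose window spans those on Days 43, 85 and 113.

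A reader might also infer that the adverse-event tables are affected, because SAP Section 9.6.1 says "AEs by week of onset will be presented". The documents do not support that. The SAP section does not refer to the Attachment 2 week row, SAP Section 5 uses the Week 0 convention, and the table layouts are in a separate shell document that is not available here. Any missing definition of onset week would exist without this discrepancy.

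What the reply does not remove is the contradiction. It is in the current operative schedule, and the one conduct rule that depends on it has no visit or day to fall back on.

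**Conclusion.** The point holds as a minor internal inconsistency. Attachment 2 labels identical study days one week apart on its two pages, the second page disagrees with the rest of the protocol and the SAP, and Section 9.6 leaves its multiple-dose boundary exposed by naming only a week.

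The consequence, if a site used the second page, is topical treatment opening a nominal 7 days (3 to 11 with tolerances) before the Day 85 PASI and sPGA, less the abstention period. That range assumes both visits take place within their printed tolerances. The number of patients affected cannot be estimated: the enrolment cap of 30 in this phase is only an upper limit, and the documents give no expected rate of topical use.

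The likelihood is low. The label does not touch the primary pharmacokinetic objective or the secondary safety objective, and a reader should not infer that the main results are at risk. Which day ought to open topical treatment is a clinical matter and is not judged here.

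**What to change.** Reconcile the two week rows of Attachment 2 to one convention, consistent with the day-to-week pairings in the rest of the protocol and the SAP. In Section 9.6, have the sponsor state the intended visit number and study day for the multiple-dose boundary, in the same form as the single-dose window, so that the rule no longer depends on a week label.

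This is protocol wording only. It changes no visit, sample, assessment or analysis, and this point needs no change to the SAP.
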